12.2.2 Definitions of Response

12.2.2.1 Target Lesions

Definitions of response for individual patients at each assessment time point for target lesions are shown in Table 2.

Table 2 Evaluation of Response in Target Lesions

Response Category	Definition
CR	Disappearance of all target lesions. Any pathological lymph nodes (whether target or non-target) must have reduction in short axis to < 10 mm.
PR	At least a 30% decrease in the sum of diameters of target lesions, taking as reference the baseline sum diameters.
PD	At least a 20% increase in the sum of diameters of target lesions, taking as reference the smallest sum on study (this includes the baseline sum if that is the smallest on study). In addition to the relative increase of 20%, the sum must also demonstrate an absolute increase of at least 5 mm. (Note: the appearance of one or more new lesions is also considered progression). For this study, PD should be confirmed at least 4 weeks later.
SD	Neither sufficient shrinkage to qualify for PR nor sufficient increase to qualify for PD, taking as reference the smallest sum diameters while on study

Abbreviations: CR, complete response; PR, partial response; PD, progressive disease; SD, stable disease

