1.0 PROTOCOL SUMMARY AND/OR SCHEMA

This is an open-label, single institution, phase Ib/phase II non-randomized trial that evaluates the safety, tolerability and anti-tumor activity of fulvestrant and Debio 1347 in patients with ER+/HER2- metastatic breast cancer (MBC) that are FGFR-amplified (as confirmed by a CLIA certified laboratory). The phase Ib portion will evaluate 2 dose cohorts (80mg (cohort/dose level 1), and one dose de-escalation cohort (60 mg dose level -1) in case dose level 1 is deemed to have intolerable toxicity. Only the dose of Debio 1347 will be de-escalated. Fulvestrant will be administered intramuscularly at standard doses. Total number of patients expected in the phase 1b portion: minimum 4 and maximum 12.

The phase 2 portion will be comprised of an optimal Simon two-stage design to determine the efficacy (defined as clinical benefit rate (CBR): overall response rate (ORR) + Stable disease (SD) \geq 24 weeks) of Debio 1347 plus fulvestrant. Patients enrolled to the phase II portion will be treated at the recommended phase 2 doses (RP2D) identified from the phase Ib portion of the study. Total number of patients expected in the phase 2 portion: minimum 18, maximum 43.

Briefly, patient's eligibility criteria will include: pre/peri/post-menopausal women and men with metastatic ER+/HER2-/FGFR-amplified breast cancer, in first or second line of treatment in the metastatic setting (phase II portion) without prior use of a FGFR inhibitor; ECOG performance status ≤ 1 , normal baseline blood counts and chemistry laboratory profile; and no intercurrent uncontrolled illness. Treatment will be given until disease progression or unacceptable toxicity. To assess the anti-tumor effect of therapy, we will estimate the overall tumor burden at baseline to which subsequent measurements (performed every 8 weeks for the first 6 months and then every 12 weeks thereafter using the Solid Tumor Response Criteria [RECIST] v1.1) will be compared.

Pharmacokinetic and pharmacodynamic data will be obtained throughout the phase Ib/Phase II portion of the study. A baseline biopsy of a metastatic site will be required for all the patients enrolled on the trial, with the acquisition of at least 3 fragments of a core biopsy and in addition archival tissue will also be obtained, whenever available. Tissue will be evaluated for FGFR amplifications by FISH and protein and mRNA expression in collaboration with [name].

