8.1 PRETREATMENT EVALUATION

To be completed within 28 days of starting Cycle 1 Day1 (unless otherwise indicated):

- Signed informed consent for study participation
- History and physical examination including height, weight, vital signs (temperature, pulse rate, respiratory rate, blood pressure, pulse oximetry), performance status (ECOG), and review of pathology and concomitant medications: medications taken within 28 days of starting Debio 1347 and fulvestrant
- Urine or serum pregnancy test for all women of childbearing potential. If the test result is positive related to pregnancy, the patient will not be allowed to participate in this study
- CBC with differential and platelet count
- Complete metabolic panel (sodium, potassium, chloride, bicarbonate, BUN, creatinine, glucose, total protein, albumin, bilirubin, alkaline phosphatase, AST, ALT, calcium)
- Magnesium

- Phosphorous
- γ GTP
- CPK
- CRP
- Uric Acid
- LDH
- Calcium regulating hormones (whole-PTH, 1,25(OH)2D, PTHrP)
- PT/INR & aPTT
- Serology for HepBsAg, HepBcAb, HIV and hepatitis C antibody (negative test acceptable prior to screening period)
- Tumor markers: CEA and Ca 15-3
- Urinalysis including urinary protein, blood, glucose, urobilinogen, pH, sediment, creatinine, calcium (CA), phosphate
- 12-lead Electrocardiogram (EKG)
- ECHO
- Complete ophthalmologic examination. The examination will be interpreted by a qualified ophthalmologist, including visual acuity testing, slit-lamp ophthalmoscopy and indirect ophthalmoscopy.
- CT scan with contrast (chest, abdomen and pelvis). If patient is unable to receive CT contrast, or the abdominal/pelvic target lesion is indeterminate on CT scan, then MRI with contrast (abdomen and pelvis) plus CT chest without contrast may be performed.
- A baseline brain MRI or CT scan with contrast (the same method of imaging done at baseline should be done throughout the study at indicated time points) is required only for patients with a history of brain metastases
- Research blood samples: for PK and cfDNA as detailed in section 12.0
- Baseline tumor biopsies will be obtained during screening for all patients enrolled in the study

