- f) Calcium regulating hormone assessments (whole-PTH, 1,25(OH) 2D, PTHrP) will be performed every cycle until Cycle 3 and every 3 cycles thereafter.
- g) Ophthalmological tests to be repeated as clinically indicated during treatment. Complete ophthalmologic examinations will be performed at screening and, as soon as clinically indicated, if a patient reports any visual abnormality. Complete ophthalmologic examination will be performed and interpreted by a qualified ophthalmologist, including visual acuity testing, slit-lamp ophthalmoscopy and indirect ophthalmoscopy. At the final visit and 28 days after the last dose, slit-lamp ophthalmoscopy will be performed.
- h) Tumor assessments (patients with a history of brain mets will be required to have brain CT scans with contrast or MRIs) to be performed every 8 weeks for 48 weeks (i.e. cycle 2, 4, 6 between days 22 and 28) and then every 12 weeks thereafter (i.e. cycle 9, 12, 15 again between days 22 and 28 etc.).
- i) Plasma samples for cfDNA analysis will be collected prior to dosing on cycle 1, cycle 1 day 15, day 1 of C3 and then at EOT.
- j) Plasma samples for PK will be collected both during phase 1 and 2. Phase 1 PK will be collected prior to dosing on day 1 and 15 of cycle 1 and then day 1 of each cycle thereafter. Phase 2 PK will be collected prior to dosing on day 15 of cycle 1 and day 1 of cycle 2.

k) Baseline tumor biopsies will be obtained during screening for all patients enrolled in the study, at least three fragments on a core biopsy

l) Documented negative tests prior to screening period is acceptable.

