12.2 Tumor Response Evaluation

12.2.1 Designation of Target and Non-Target Lesions

When more than one measurable lesion is present at baseline, all lesions, up to a maximum of 5 lesions (and a maximum of 2 lesions per involved organ) representative of all involved organs should be identified as target lesions and will be recorded and measured at baseline. In the current study, the baseline measurement will be based on the scans and measurements taken at the end of the pre-study standard chemotherapy, as submitted by the investigator.

Target lesions should be selected on the basis of their size (lesions with longest diameter) and be representative of all involved organs, but in addition should be those that lend themselves to reproducible repeated measurements. It may be the case that on occasion, the largest lesion does not lend itself to reproducible measurement; in such cases, the next largest lesion that can be reproducibly measured should be selected.

A sum of the diameters (longest for non-nodal lesions, short axis for nodal lesions) for all target lesions will be calculated and reported as the baseline sum diameters. The baseline sum diameters will be used as the reference to characterize any objective changes in the measurable dimension of disease.

All other lesions or sites of disease (i.e., non-measurable lesions), including pathological lymph nodes, should be identified as non-target lesions. Measurements of non-target lesions, even if measurable, are not required, as they are intended to be assessed qualitatively and should be designated as present or absent at baseline. It is also possible to record multiple non-target lesions in the same organ as a single item, e.g., "multiple enlarged pelvic lymph nodes."

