12.2.2.4.1 Additional Notes Relevant to Designations of Disease Progression

Per RECIST v.1.1, patients with a global deterioration of health status requiring discontinuation of treatment without objective evidence of disease progression should be reported as

“symptomatic deterioration,” and every effort should be made to document objective progression even after discontinuation of treatment. Symptomatic deterioration is not a descriptor of an objective response; it is a reason for stopping study therapy. The objective response of such subjects is to be determined by evaluation of target and non-target disease as shown in Table 17 and Table 18. In the current study, scans are to be done every 3 cycles and at any time deemed appropriate by the investigator (i.e., when progression is suspected). PD at first response scan must be confirmed at least 4 weeks later.

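### Section 12's study-specific response rules conflict with each other and with the rest of the protocol, so one patient can be scored two ways on the primary clinical benefit rate

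*Combined protocol and SAP*

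**What the plan says.** **Primary endpoint.** Section 14.0 counts CR, PR, or SD of at least 24 weeks. The trial stops at 2 or fewer of 18 and is positive at 8 or more of 43.

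**Confirming progression.** Section 12.2.2.1, Table 2: "For this study, PD should be confirmed at least 4 weeks later". Section 12.2.2.4.1: "PD at first response scan must be confirmed at least 4 weeks later". Table 3 (non-target lesions), Section 12.2.2.3 (new lesions) and Table 4 (overall response) call PD without asking for confirmation.

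**Baseline.** Section 12.2.1: "the baseline measurement will be based on the scans and measurements taken at the end of the pre-study standard chemotherapy". Section 8.1 lists the CT scan among procedures "To be completed within 28 days of starting Cycle 1 Day1".

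**Measurable disease.** Section 6.2 admits measurable or evaluable disease and lytic or mixed bone lesions. Section 12.3.3 puts non-measurable disease in the efficacy population. The special notes on non-target progression in Section 12.2.2 describe the study as one with concurrent measurable disease.

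**Scan schedule.** Section 12.2.2.4.1: "scans are to be done every 3 cycles and at any time deemed appropriate by the investigator". Section 10.1, footnote h: "every 8 weeks for 48 weeks (i.e. cycle 2, 4, 6 between days 22 and 28", "then every 12 weeks thereafter (i.e. cycle 9, 12, 15 again between days 22 and 28 etc". Section 1.0: "performed every 8 weeks for the first 6 months and then every 12 weeks thereafter".

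**The concern.** CBR is a count set against fixed boundaries, so the rule that sorts each patient into benefit or no benefit is part of the decision rule. Where two current passages sort the same patient differently, the result depends on which one the assessor follows. In an open-label, single-arm trial, a choice made after outcomes are known is hard to defend.

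The errors could run either way. Dating PD at a confirming scan, or ignoring PD that was never re-scanned, would raise CBR. Leaving stable patients without target lesions with no route to SD would lower it. PFS and TTP event dates are open in the same way.

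**Working it through.** **1. The design as stated.** Inputs from Section 14.0: p0 = 0.10, p1 = 0.25, stop if X1 ≤ 2 of 18, positive if the total is ≥ 8 of 43.

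- Early termination at 10%: P(X1 ≤ 2 | 18, 0.10) = 0.734 (stated 0.73).
- Type I error: P(X1 ≥ 3 and total ≥ 8 | 0.10) = 0.048 (stated 5%).
- Power: the same probability at 0.25 = 0.800 (stated 80%).

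An exhaustive search returns the same design as optimal. The design is not in question.

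**2. Confirmation.** The two confirmation sentences agree at the first scan. At later scans, including cycle 6, Table 2 still asks for confirmation and Section 12.2.2.4.1 does not. Take a patient whose target-lesion PD is first seen at a later scan and never re-scanned. Under Section 12.2.2.4.1 this is PD; under Table 2 it may not be. Table 2's sentence follows a note that new lesions are progression, so it may or may not reach new-lesion PD, which Section 12.2.2.3 calls outright.

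**3. The 24 weeks.** Assume undelayed 28-day cycles. Cycle 6, days 22–28, is study days 5×28+22 = 162 to 6×28 = 168. Twenty-four weeks is 168 days.

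| Origin and counting | Cycle-6 window | Against 168 days |
|---|---|---|
| C1D1, elapsed days | 161–167 | 1–7 short |
| C1D1 counted as day 1 | 162–168 | 0–6 short |
| Screening scan, day −1 to day −28 (no day 0) | 162–195 | 6 short to 27 over |

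The last row is 161+1 = 162 and 167+28 = 195. A scan confirming cycle-6 PD comes no earlier than 161+28 = 189 elapsed days from C1D1. With C1D1 as origin and elapsed days, PD first seen at cycle 6 is therefore short of 24 weeks if dated at that scan and past it if dated at the confirming scan. With an early screening scan as origin, even first-scan dating can exceed 168 days.

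**4. No target lesions.** Table 2 defines SD by target-lesion sums. Table 4 has no non-PD row for a patient without target lesions. Section 14.0 does not say whether non-CR/non-PD for 24 weeks is clinical benefit.

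**5. Scan interval (secondary).** Footnote h's listed cycles 2, 4, 6 cover 6×4 = 24 weeks, which fits Section 1.0; only its 48-week figure is out of line. Every 3 cycles gives cycles 3, 6, 9. All versions include cycle 6. What changes is which scan is first (cycle 2 or 3), and so who has the on-treatment assessment that Section 12.3.3 needs and who is replaced under Section 9.5.

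**6. How close the boundaries are.** These are properties of the design under perfect scoring, not rates of mis-scoring.

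| | True rate 10% | True rate 25% |
|---|---|---|
| Exactly 2 of 18 | 0.284 | 0.096 |
| Exactly 3 of 18 | 0.168 | 0.170 |
| Stage 1 passed, total 7 of 43 | 0.046 | 0.040 |
| Stage 1 passed, total 8 of 43 | 0.027 | 0.070 |

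**7. Illustrations under assumed shares.** The documents give none.

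- One extra patient in 43 scored as benefit, on average: 0.10 + 1/43 = 0.123; type I error 0.12.
- A share b without target lesions, none able to count: the rate is 0.25(1−b). For b = 0.1, 0.2, 0.3 this is 0.225, 0.200, 0.175; power 0.70, 0.56, 0.41.

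**The case against.** **The two confirmation sentences can be read together.** Table 2 says should and Section 12.2.2.4.1 says must. Confirming every PD satisfies both. That stands as a possible reading, but it is not written down, and it leaves the PD date and never-re-scanned PD open.

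**Appendix B may fill the gap for patients without target lesions.** Section 12.0 calls its content a summary, and the full RECIST 1.1 article is an appendix that was not supplied. A reader might infer that these patients cannot be scored at all. The documents do not support that: Section 12.3.3 includes them, Table 3 gives them a CR category, and Appendix B may give the rest. What remains is that the assumption of measurable disease contradicts Sections 6.2 and 12.3.3, and that no supplied passage links non-CR/non-PD to CBR.

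**The scan-interval conflict hardly reaches CBR.** This is largely right, since every version has a cycle-6 scan. Its effect is indirect.

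**The cycle-6 scan does not always miss 24 weeks.** A reader might infer that it does. That depends on the origin and on how days are counted, neither of which is stated.

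**The magnitudes do not measure the defect.** This also stands. A reader might infer that the true type I error is 0.12 or that power is 0.41. Both follow from assumed shares, the power figures are a worst case in which no patient without target lesions counts, and the two effects can partly cancel.

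**Conclusion.** The rules are wrong as written and should be fixed. The firm findings are the differing confirmation rules after the first scan with no dating rule, a baseline tied to a chemotherapy that eligibility does not require, and an assumption of measurable disease that eligibility contradicts. The unstated start of the 24 weeks is a gap that matters because the cycle-6 window sits at the threshold. The scan-interval mismatch is secondary.

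Following the text can give one patient two CBR results, and a single patient separates 2 from 3 of 18 and 7 from 8 of 43. Beyond that the size is not established: neither the number of patients affected nor the net direction can be derived from the documents. The day counts assume undelayed 28-day cycles. None of this impugns the two-stage design.

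**What to change.** For endpoint scoring only, and before the stage 1 count:

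- **Progression.** Reconcile Tables 2 and 3 and Sections 12.2.2.3 and 12.2.2.4.1 into one rule that says whether target, non-target and new-lesion PD each need confirmation. For CBR, PFS and TTP, date confirmed PD at the first scan that showed it. State how PD that is never re-scanned, or that a later scan does not confirm, is scored; counting never-re-scanned PD as PD is the conservative choice.
- **Baseline.** Replace the baseline sentence in Section 12.2.1 with the Section 8.1 screening scan.
- **No target lesions.** Correct the measurable-disease assumption, add Table 4 rows for these patients, and state whether non-CR/non-PD for at least 24 weeks counts in CBR.
- **24 weeks.** State the origin and the counting of days, and whether a scan in the cycle-6 window satisfies the requirement.
- **Schedule.** Reconcile the 3-cycle interval in Section 12.2.2.4.1 and the 48-week figure in footnote h with Section 1.0.

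Separately, Section 10.1.3 ends treatment on documented progression while Section 13.1 refers to confirmed radiographic progression. The two must be reconciled; no view is taken here on which is right.

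The cost is protocol wording. The 18 and 43 patients and both boundaries stay. CBR and PFS may look slightly less favourable under first-scan dating.

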12.2.2.1.1 Lymph Nodes as Target Lesions

Please refer to RECIST v.1.1 in Appendix B for special notes on the assessment of lymph nodes as target lesions, lesions that become too small to measure, and lesions that split or coalesce after treatment.

12.2.2.2 Non-target Lesions

Definitions of response for individual patients at each assessment time point for non-target lesions are shown in Table 18. Non-target lesions, even if measurable, are to be evaluated qualitatively, as noted above, and are to be designated as CR, non-CR/non-PD, or PD, as defined in Table 3.

Table 3 Evaluation of Response at Each Time Point in Non-target Lesions

Response Category	Definition
CR	Disappearance of all non-target lesions and normalization of tumor marker level. All lymph nodes must be non-pathological in size (<10 mm short axis).
Non-CR/Non-PD	Persistence of one or more non-target lesion(s) and/or maintenance of tumor marker level above the normal limits.
PD	Unequivocal progression (see comments below) of existing non-target lesions. (Note: the appearance of one or more new lesions is also considered progression). ^a

Abbreviations: CR, complete response; SD, stable disease; PD, progressive disease.

^a Although a clear progression of “non-target” lesions only is exceptional, in such circumstances, the opinion of the treating physician should prevail.

12.2.2.1 Special Notes on Designation of Progression in Non-Target Disease

The concept of progression of non-target disease in the setting of concurrent measurable disease as in this study requires further explanation. In this setting, to assign unequivocal progression on the basis of the non-target disease (see determination of overall response in Section 0), there must be an overall level of substantial worsening in non-target disease such that, even in the presence of SD or PR in the target disease, the overall tumor burden has increased sufficiently to warrant discontinuation of therapy (see examples in the RECIST v.1.1 guidelines in Appendix B). A modest increase in the size of one or more non-target lesions is usually not sufficient to qualify for a designation as unequivocal progression. The designation of overall progression solely on the basis of change in non-target disease in the face of SD or PR of target disease will therefore be extremely rare.

12.2.2.3 New Lesions

The appearance of new malignant lesions denotes disease progression. Refer to RECIST v.1.1 in Appendix B for notes concerning the detection of new lesions.

12.2.2.4 Missing Data

When no imaging/measurement is done at all at a particular time point, the subject is not evaluable (NE) at that time point. If only a subset of lesion measurements is made at an assessment, usually the case is also considered NE at that time point, unless a convincing argument can be made that the contribution of the individual missing lesions would not change the assigned time point response. This would be most likely to happen in the case of PD. For example, if a subject had a baseline sum of 50 mm with three measured lesions and at the assessment only two lesions were assessed, but those gave a sum of 80 mm, the subject will have achieved PD status regardless of the contribution of the missing lesion measurement.

12.2.2.4.1 Additional Notes Relevant to Designations of Disease Progression

Per RECIST v.1.1, patients with a global deterioration of health status requiring discontinuation of treatment without objective evidence of disease progression should be reported as

“symptomatic deterioration,” and every effort should be made to document objective progression even after discontinuation of treatment. Symptomatic deterioration is not a descriptor of an objective response; it is a reason for stopping study therapy. The objective response of such subjects is to be determined by evaluation of target and non-target disease as shown in Table 17 and Table 18. In the current study, scans are to be done every 3 cycles and at any time deemed appropriate by the investigator (i.e., when progression is suspected). PD at first response scan must be confirmed at least 4 weeks later.

12.2.2.5 Overall Response for Each Subject at Each Assessment Time Point

Overall response at each assessment time point is based on the totality of the responses for target and non-target lesions, as shown in Table 19.

Table 4 Rubric for Determination of Overall Response at Each Assessment Time Point for Each Patient

Target Lesions	Non-target Lesions	New Lesions	Overall Response
CR	CR	No	CR
CR	Non-CR/non-PD	No	PR
CR	Not evaluated	No	PR
PR	Non-PD or not all evaluated	No	PR
SD	Non-PD or not all evaluated	No	SD
Not all evaluated	Non-PD	No	NE
PD	Any	Yes or No	PD
Any	PD	Yes or No	PD
Any	Any	Yes	PD

Abbreviations: CR, complete response; PR, partial response; SD, stable disease; PD, progressive disease

